1.5.4 Schedule and Description of Participant Visits

Each of the study

participants will be first seen in the hospital during their admission for MI or after discharge in the clinic within the window of enrollment. They will then be followed with one phone call and one clinic visit. The schedule for testing and data collection is outlined in Table 2. The visit timeline and windows for visits are provided in Chapter 3 of the Operations Manual.

• *Enrollment Visit (V0):* Begins during the participant's hospitalization for MI
 Table 2: Scheduled visits and data collection

DATA COLLECTED AND		VISITS			
TESTING PERFORMED		Post-discharge			
	V0	V1	V2	Registry	
	Enrollment	1 Month Phone	3 Month Visit		
Screening and Medical History	Х				
Vital signs, discharge meds & diagnoses (from chart)	X				
Symptom Checklist		Х	Х		
Medication Review	Х	Х	Х		
Medical Care Utilization		Х	Х	Х	
Vital Status			Х	Х	
QOL Survey			Х		
Test Reports 12 lead ECG Local Labs 	From Medical Record				
Echocardiography	From Medical Record		From Medical Record	From Medical Record	
Home Monitoring LifeVest 	upload baseline at fitting		in 1 st week, 1 weekly		

or within the window of enrollment after discharge. Participants who meet enrollment criteria will be asked to participate in the study after they are medically stable. After consent for VEST, they will be enrolled and randomized to vest or no vest. If randomized to vest, they may leave the hospital with the vest. The enrollment visit will involve collection of information and data abstracted from the hospital chart.

- *1 Month Follow-up Telephone Call (V1)*: All participants will be contacted by phone to gather follow-up data. Participants will be asked about changes in medication, intervening hospitalization or visits to the emergency department, any problems with the vest (if randomized to the LifeVest) and a simple symptom checklist.
- *3 Month Visit (V2):* All participants will be seen for clinical data collection/final visit. Participants will be asked about changes in medication, intervening hospitalization or visits to the emergency department, any problems with the vest (if randomized to the LifeVest), and a simple symptom checklist. The patient's most recent EF will be extracted from his/her medical record and assessment of qualification for primary prevention ICD will also be recorded. A Quality of Life survey will be

Protocol

mailed to the participant prior to this visit for self-administration and returned to the clinical site during this visit.

• *VEST Registry Follow-up Telephone Call:* Participants will be contacted by phone at least yearly to gather follow-up data. Participants will be asked about changes in medication, intervening hospitalizations, and simple follow-up questions regarding ICD/pacemaker device implantation.

Continuous Participant Monitoring (during the study period: V0-V2)

In addition to the visits described above, participants randomized to LifeVest will have continuous remote monitoring via the LifeVest.

Monitoring Capabilities and Data Collection from LifeVest: The LifeVest performs constant ECG monitoring while it is worn. It records all ventricular tachyarrhythmias that last more than 15 seconds and asystolic events (<20 beats per minute). Bradyarrhythmias (<40 bpm) are logged but no ECG is recorded. It also compiles compliance data by recording the amount of the time the LifeVest is worn each day. This data will be uploaded via modem and phone line. After initial setup, the coordinator or fitter (from ZOLL Lifecor) will upload the participant's baseline data, then the participant will upload (from home) every other day for a total of 3 times during the first week and then subsequently on a weekly basis. The DCC will notify enrolling sites if participants are not sending scheduled transmissions. The enrolling sites can then contact participants to discover problems and encourage compliance. Sites with persistent or numerous poorly compliant participants will be visited and their staff re-trained.

The participant's compliance to the visit schedule will be continuously monitored on the study website by clinical site. The CCC will review visit compliance reports with the clinical sites on the Quality Control Committee conference calls/meetings to identify problems and recommend corrective action. If a participant misses a scheduled visit, clinic staff will contact him/her immediately to review the reasons for the missed visit, to identify any barriers that can be corrected, and to reschedule the visit.

1.5.5 Interventions in VEST

Participants will be randomized in a 2:1 fashion to either receive optimal post-MI and CHF medical therapy plus a wearable defibrillator (LifeVest) or optimal post-MI and CHF medical therapy alone for 90 days. Participants randomized to the LifeVest will be fit with the LifeVest ideally before they are discharged from the hospital or clinic, but the fitting may occur at the participant's home within 7 days post discharge from index MI.

Compliance: Prior to consent to participate in the study, potential participants may be shown the LifeVest and given an opportunity to try it on. Participants will be told that they will be expected to wear the LifeVest for at least 23 hours a day for 3 months. Site coordinators will be trained on how to use the LifeVest and will help teach participants how to use the LifeVest properly to enhance compliance. Participants will be fully trained on how to put the LifeVest on and off, and how to temporarily disable the LifeVest by pushing a button to prevent inappropriate or premature shock. Additionally, participants will be trained how to maintain the LifeVest and determine if it is functioning normally as well as how to transmit data from the LifeVest monitor via the integrated modem over a phone line. Participants, regardless of group assignment, will receive optimal medical therapy based on current AHA/ACC Guidelines unless there is a contraindication^{7, 8}.

Participants will be urged to wear the LifeVest continuously after hospital discharge for at least 3 months (or until ICD implantation). They will be instructed to take the LifeVest off only for bathing or showering. Participants will send data from the LifeVest monitor via modem 3 times a week for the first week and on a weekly basis thereafter. These data will include the compliance of wearing the LifeVest, Holter data, arrhythmia occurrence and shocks (delivered and aborted). Site coordinators will contact participants who don't transmit on schedule or who wear the LifeVest <20 hours per day for 2

Protocol

consecutive days by phone to discuss any problems participants might be experiencing with the purpose of obtaining excellent overall compliance rates. For sites with poor compliance rates, the following remedial actions will be taken: 1) discussions with site coordinator; 2) engagement of ZOLL Lifecor staff and site visit for coordinator training, if needed; 3) engagement of ZOLL Lifecor staff for fitting of participants.

Blinding to treatment assignment: Participants and clinicians will not be blinded to treatment assignment (LifeVest versus no LifeVest). Since the primary outcome in *VEST* is sudden death and death due to ventricular arrhythmia, it is unlikely that this outcome would be significantly affected by either participant or clinician knowledge of treatment assignment.

Blinding to arrhythmias: Clinicians will be blinded to most arrhythmia recordings from the LifeVest in the group assigned to wear the LifeVest. This is necessary to prevent co-interventions with inappropriate anti-arrhythmic drugs or early implantation of an ICD. There are provisions for unblinding when clinically indicated, as detailed in Chapter 6 of the Operations Manual. Two types of unblinding will occur:

1) Automatic unblinding, generated by the DCC or ZOLL, which will result in electronic notification to the site and sending of LifeVest monitoring strips. Automatic unblinding will be initiated if any of the following events occurs:

- Participant receives a shock
- LifeVest alarms, but participant averts a shock or the rhythm spontaneously terminates if the rhythm lasts > 30 seconds
- Asystole or Bradycardia less than 20 bpm

2) Clinical sites can request unblinding and receive LifeVest strips under the following circumstances:

- Participant suffers a cardiac arrest, or reports receiving a shock or LifeVest alarm
- Participant complains of syncope or pre-syncope
- Participant complains of palpitations
- Physician deems it to be medically necessary (a protocol deviation may be reported)

The procedure for requesting these strips will require a case report form (completed by ZOLL personnel) with a diagnosis or rationale (as outlined above), the date range of strips requested and a follow-up form that documents any treatment changes resulting from viewing these strips.

Crossovers

Participants randomized to the control arm of VEST should not wear a LifeVest during the 3 month VEST follow-up period; use of a LifeVest by a control participant will be recorded as a protocol deviation.

Treatment of Participants Who Receive a LifeVest Shock

Evaluation and treatment of participants who receive a shock while wearing the LifeVest will be determined by the treating physicians. Recommendations for possible evaluation strategies and treatment will be included in the Operations Manual (Chapter Guidelines for Care of the Medical Treatment). This may include the possibility of assessing for recurrent ischemia, treatment of arrhythmias such as atrial fibrillation or titration of medication.

Early ICD Implantation

It is recognized that some participants will develop indications for ICD implantation during the 3 month VEST portion of the study. Given the short follow-up of only 3 months, we anticipate that this will be a rare event. The protocol provides for participants in the control (non-LifeVest group) and the intervention group (LifeVest group) who suffer an aborted cardiac arrest subsequent to the qualifying

Protocol

MI/hospitalization to be implanted with an ICD. Participants with syncope and >30 seconds of VT may also have an ICD implant.

The following are NOT considered appropriate reasons for early ICD implantation and if elected by the treating physician will be considered protocol deviations:

- Malfunction of the LifeVest (Poor sensing or inappropriate detection/shock delivery)
- Poor participant compliance
- Non-sustained ventricular arrhythmias (<30 seconds)
- Asymptomatic ventricular arrhythmias

In addition, a detailed algorithm for initiation of anti-arrhythmic drugs for ventricular arrhythmias and atrial fibrillation based on ACC/AHA Guidelines will be provided in the operations manual.^{6, 9} Deviations from these algorithms that are elected by the attending physician will be considered a protocol deviation.

1.5.6 Randomization

Participants will be randomized in a 2:1 ratio to either receive the LifeVest or not, respectively. Randomization will be stratified and blocked to protect against chance maldistribution of important predictors. Stratification will be by ejection fraction ($\leq 25\%$ vs. > 25%) and by revascularization status (i.e., None/PCI/CABG), both known strong predictors of mortality, and by clinical site to protect against maldistribution of other unmeasured potential confounders that might be unequally distributed at different clinical sites. Randomization blocks will vary in size to protect against *predictability* of randomization assignment within clinical site/EF/revascularization strata. Block size will vary from 3 to 6, allowing for a maximum absolute deviation of 4 participants from the exact 2:1 ratio in any given site/EF/revascularization stratum. Separate tables for each stratum will be pre-generated (by existing routines developed by the Senior Statistician for the study), encrypted, and accessible only to the Senior Statistician and the DCC Data Analyst.

The DCC will implement a web-based interface that clinical sites will use to obtain randomization assignments for each enrolled participant after completion of the Enrollment Visit. Clinical sites will access the randomization website using a secure password, and will be prompted to attest that all entrance criteria are met and that informed consent has been obtained. Each inclusion and exclusion criterion will require active attestation to minimize errors of omission. Once entry criteria are verified electronically, the recruiter will be shown a "randomize" button, and will receive the assignment ("Wear LifeVest" or "Do Not Wear LifeVest") upon activating the button since participants and clinical site clinicians are not blinded to treatment assignment. After randomization, the group assignment may be printed by the clinical sites from the website along with group-specific study instructions for physicians and participants.

If there is any question regarding eligibility for randomization, the clinical site personnel will contact the CCC for adjudication prior to seeking randomization. Every effort will be made to minimize protocol deviations regarding participant eligibility for the study, including quality control procedures to assure that the ejection fraction (EF) entry criterion is accurate.

1.5.7 Participant Retention

We will make every effort to ensure that participants are not lost to follow-up nor drop out of the study. At the initial screening and enrollment visit, the clinical site will record identifying information including address, phone number, social security number and the name, address and phone number of one family member and two close friends able to locate the participant.

We do not expect many participants to be lost to follow-up given the short 3 month time frame. All the participants will be recovering from a recent MI; therefore, they are less likely to travel far or be non-compliant. Two thirds of the participants will also be wearing a LifeVest during these 3 months. The LifeVest will be a reminder to participants that they are in the study and need to maintain close follow-up with the study coordinators. In addition, participants wearing the LifeVest will be required to send data via a modem (integrated into the LifeVest monitor) on a weekly basis. This will allow clinical sites to track participants on a weekly basis. The Data Management System will identify participants who have missed transmissions and post reports on the study website accessed by site coordinators. These will be followed up by e-mail alerts.

6

1.5.8 Predictor Variables

The primary predictor variable will simply be randomization to LifeVest or no LifeVest.

1.5.9 Outcome Variables

The outcome measures are outlined in Table 3. The primary outcome is sudden death and death due to ventricular arrhythmia at 3 months (90 days) after randomization. We will use the following definition of Sudden Death:

For witnessed deaths, sudden cardiac death will be defined as an unexpected, non-traumatic, nonself-inflicted fatality in otherwise stable participants who die within one hour of the onset of the terminal symptoms. For persons dying more than one hour after a cardiac arrest from a ventricular arrhythmia, the Non-Sudden Death due to Ventricular Arrhythmia category should be used.

For unwitnessed deaths, participants will meet the definition of sudden death if they are found dead within 24 hours of being well, assuming there is no evidence of another cause of death during that time period. Device arrhythmia and autopsy results may be used when available. For unwitnessed deaths when the participant was found dead more than 24 hours after last being seen, no device arrhythmia data are available, no autopsy results are available and no other information is available regarding the cause of death, the Indeterminate category should be used.

We also include non-sudden deaths due to ventricular arrhythmia in the primary outcome definition. Deaths are categorized as such when a person suffers a cardiac arrest from an acute ventricular arrhythmia, is resuscitated and admitted to the intensive care unit, and then dies several days after the arrest from complications (e.g., neurological damage). Secondary outcomes for VEST are total mortality, non-sudden death and other cause-specific mortality (non-sudden fatal MI, other cardiac death, non-cardiac death, and indeterminate cause of death), hospitalization for MI, congestive heart failure, stroke/transient ischemic attack, ventricular arrhythmias, adverse events, LifeVest compliance, eventual ICD implantation, quality of life, and resource utilization/cost. The wearable defibrillator can do continuous ECG recording and monitor time worn. Therefore, data for several of the secondary outcomes that are analyzed within the intervention group will come from the LifeVest transmissions.

Outcome Adjudication: The DCC will direct the adjudication of study outcomes. Assigning cause-specific mortality, as is required for the primary VEST outcome and a number of important secondary endpoints for VEST, can be difficult. Cardiac electrophysiologists actively engaged in clinically relevant patient care will be employed to provide expert opinions regarding these endpoints. The Endpoints Director will manage the adjudication process designed to categorize arrhythmias and deaths appropriately, minimize bias by blinding adjudicators to treatment assignment, and protect against unnecessary disclosure of protected health information. Table 3 lists the primary and secondary outcomes, the data source, and whether or not each endpoint requires adjudication. Definitions for each endpoint are provide below.

Cause-specific Mortality and Non-Fatal Cardiovascular Events: Deaths will be reported by family members or clinicians, or detected by clinical sites when study participants fail to show up for scheduled examinations or miss scheduled data transmissions. Social security death index searches will be performed for all participants lost to follow-up for whom vital status is unknown in the U.S.. Hospitalizations will be reported by participants at or between scheduled examinations or phone calls. Sites will notify the DCC within 48 hours of learning about a death or cardiovascular hospitalization, and will then have eight weeks to obtain a death certificate; all discharge summaries for any hospitalizations occurring within 1 month of the index death/hospitalization, and narratives from personal contacts of deceased participants (listed at recruitment) regarding manner and circumstances of death. All personal identifiers and mention of treatment assignment (for the VEST arm) will be carefully stripped by clinical site staff to the extent possible. For all deaths, the DCC will redact any mention of the LifeVest in participants assigned to VEST, and add fake redaction in participants assigned to NO VEST so that adjudication of cause of death will be blinded. ECG data from the LifeVest will NOT be used to adjudicate fatal outcomes for VEST,

Protocol

because this information will not be available on participants without a LifeVest, and use might induce bias from differential measurement error. Complete packets will be assembled by the DCC and read independently by two adjudicators. Every death will be categorized according to the cause-specific mortality and non-fatal cardiovascular event categories described in Table 3. Disagreements will be resolved by consensus, involving a third adjudicator when required.

Ventricular Arrhythmias: Electronic rhythm strips recorded by the LifeVest will be uploaded to the study database via electronic data transfer from ZOLL. Strips will be presented to adjudicators in batches, with study ID numbers and adjudication forms and read independently by two cardiac electrophysiologists. Adjudicators will determine whether the LifeVest therapy was "appropriate" or "inappropriate" based primarily on the presence or absence of a true ventricular arrhythmia. Discordances will be resolved by consensus, involving a third adjudicator when required.

Quality of Life: Quality of life outcomes will be measured using self-administered questionnaires mailed to participants 1-2 weeks prior to the 3 month visit. QOL will be assessed using the SF-36 for health related quality of life, the CES-D to measure depression, the Spielberger STAI to measure anxiety, and the MOS sleep scale to measure sleep patterns. The EQ-5D will be administered to measure subjective health status, and the International Physical Activity Questionnaire (IPAQ) short format for physical activity. The Florida Patient Acceptance Scale (FPAS) will be included to measure device acceptance in those randomized to the LifeVest.

Economic Outcomes: Cardiovascular hospitalizations, visits to emergency rooms, unscheduled cardiovascular outpatient visits and adverse events will be collected at the follow-up visits by self-report, including the reasons for admission and length of stay. All admissions will be assigned to a DRG based on participant report and review of medical records obtained to document clinical outcomes. The number of physician visits, major tests, and medications will be collected using a brief survey. For VEST, we will compare costs over follow-up between participants assigned to the LifeVest and those assigned to usual care. We will analyze whether the costs of management, apart from the cost of the LifeVest itself, are lower in the vest assigned participants. This approach will allow us to determine if there are any cost savings in the VEST arm participants that will offset the expected, planned costs of the intervention. In a secondary analysis, we will compare total cost (i.e., costs including the cost of the LifeVest) between the two randomized groups, and calculate confidence limits on the cost difference between the two groups using a bootstrap resampling approach.

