+ - Includes information from medical records, death certificates, interviews of next-of-kin or personal physicians, and National Death Index searches

VF - Ventricular fibrillation; VT - Ventricular tachycardia; SVT - Supraventricular tachycardia; ICD - Implantable cardioverter defibrillator

stratified by length of follow-up period (to account for the higher expected rate in patients with 90 day follow-up), and randomization stratum, as jointly defined by EF and receipt of PCI and/or CABG during the hospitalization for the index MI.

We will also conduct a secondary "modified intention-to-treat" analysis of sudden death and death due to ventricular arrhythmia, total mortality, and other secondary outcomes. For this analysis, follow-up time will start at the time of discharge instead of randomization, and end 60/90 days after discharge, and participants who are randomized but die before discharge from the index hospitalization will be excluded. For death outcomes, this analysis will use the stratified exact methods specified for the primary analysis; for more common secondary outcomes, asymptotic methods will be considered.

We will also analyze treatment effects on overall mortality and non-sudden death, non-fatal cardiovascular events, ventricular arrhythmias, adverse events, LifeVest compliance, ICD implantation, quality of life and resource utilization/cost. For rare outcomes, exact methods will be used, as for the primary endpoint. For VEST therapies and hospitalizations, we will use the Anderson-Gill extension of the Cox model for repeated events, with robust standard errors, to better capture information from high-risk participants with repeated VEST therapies or hospitalizations.

We will also conduct a secondary, "as treated" analysis of sudden death and death due to ventricular arrhythmia, total mortality, and other secondary outcomes. The primary ITT analysis will estimate effectiveness of the vest, averaged over variations in compliance. We will attempt to estimate the efficacy of the vest for prevention of sudden death and death due to ventricular arrhythmia as well as total mortality using survival models treating observed vest use as a time-dependent covariate. For sudden death and death due to ventricular arrhythmia, we will

6

Protocol

use a Fine-Gray model treating other deaths as competing risks; a standard Cox model will be used for total mortality.

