3. Inverse weighting to deal with indeterminate cause of death and missing vital status. In the primary analysis, participants with indeterminate cause of death or missing vital status will be assumed not to have had a primary study event. In two secondary analyses, we will restrict the analysis to deceased participants with determinate cause of death and those known to be alive, weighting these observations so that their baseline correlates of the primary outcome are representative of the entire randomized cohort. To do this, we will develop two logistic models: the first for having determinate cause of death among all patients known to have died, and the second for having known vital status among all participants. Weights will be calculated as the inverse of the product of the fitted probabilities from these two models, after assigning a fitted probability of 1 from the first model for patients known to be alive. Variables in each model will be selected, without regard to the primary outcome, from a list of known correlates of the primary study outcome, as specified by Drs. [name], [name], and [name]. To deal with missing values of the candidate variables in the *a priori* list, multiple imputation will be used, followed by averaging of the weights obtained from each of ten completed datasets. Two versions of this sensitivity analysis will be conducted, the first excluding and the second using information from the vest in

determining vital status. The weighted analyses will use procedures properly accounting for the slightly smaller sample size available for analysis.

B.2. Heterogeneity of treatment effects

• By randomization stratum. We will use a logistic model to assess heterogeneity of the treatment effect across the 6 randomization strata jointly defined by EF, PCI, and CABG, as well as across the 2 strata defined by EF and the 3 strata defined by PCI and CABG. Nominal differences across strata will be conservatively interpreted in the light of tests for interaction between treatment and stratum, using a Bonferroni-corrected two-sided alpha of 0.05/3=0.0167. In additional exploratory analysis, we will assess modification of the ITT treatment effect by drugs, NYHA class, BMI, gender, and compliance

B.3. Treatment effects on secondary endpoints

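### Does the unwitnessed-death definition let LifeVest recordings into the adjudication of deaths that the protocol elsewhere bars?

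*Combined protocol and SAP*

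**What the plan says.** Protocol 1.5.9 defines the primary outcome. For unwitnessed deaths it adds "Device arrhythmia and autopsy results may be used when available". It then reserves the Indeterminate category for participants found more than 24 hours after last being seen for whom "no device arrhythmia data are available, no autopsy results are available" and nothing else is known about the cause. Neither sentence says which device is meant.

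The Outcome Adjudication text of the same section states: "ECG data from the LifeVest will NOT be used to adjudicate fatal outcomes for VEST". The reason given is that "this information will not be available on participants without a LifeVest, and use might induce bias from differential measurement error". The same text has the data coordinating centre black out every reference to the LifeVest in vest-arm death records, insert dummy blackouts in control records, and assemble the packets that two adjudicators read independently.

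The Table 3 source note for the death outcomes reads: "Includes information from medical records, death certificates, interviews of next-of-kin or personal physicians, and National Death Index searches".

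SAP B.1.3 sets the primary-analysis rule: "participants with indeterminate cause of death or missing vital status will be assumed not to have had a primary study event". It also plans two versions of a weighted sensitivity analysis, "the first excluding and the second using information from the vest in" determining vital status.

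**The concern.** Read alone, the definition admits any device recording, and the LifeVest is the device that two thirds of participants are assigned and that monitors the ECG while worn. Section 1.5.5 shows that such recordings can exist around a death. After a shock, a rhythm of more than 30 seconds with an alarm, or asystole, the system triggers an unblinding "which will result in electronic notification to the site and sending of LifeVest monitoring strips".

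If adjudicators used those strips, a vest-arm death could be moved into the primary outcome (a recorded ventricular arrhythmia) or out of it (another rhythm). An otherwise identical control death could not be moved. That is the differential measurement error the protocol itself names, and it would fall on the primary endpoint. The direction is not fixed: moves in dilute the apparent benefit, and moves out exaggerate it. The SAP's split by vest information does not settle the matter, because it concerns vital status and not cause of death.

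**Working it through.** The plan gives no figure on this point to reproduce. The main check is textual; the arithmetic afterwards only sizes what a breach would do.

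**Can both rules be followed?**

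1. *Scope.* The definition is permissive and general. The ban is mandatory, names the LifeVest and applies to all fatal outcomes. Both stand in section 1.5.9, so a reader of the definition meets the ban in the same section.
2. *Is there another meaning for device?* Yes. Table 3 lists ICD/Reveal as a source for time to death after the first VT/VF episode. Section 1.5.5 (Early ICD Implantation) provides for an ICD during follow-up in either arm. Table 1 excludes existing unipolar pacemakers only, so others may be present. With that meaning the sentences do not conflict.
3. *Does anything else admit LifeVest data to cause of death?* No. The Table 3 note for deaths omits it. The LifeVest is the listed source only for LifeVest events and vest compliance.
4. *Can a strip reach an adjudicator?* Sites supply the death certificate, discharge summaries and narratives from personal contacts. The coordinating centre redacts and builds the packet. Section 1.5.5 sends strips to the clinical site, not to a death packet. An identified LifeVest strip in a packet would break the ban and also unblind the readers.
5. *How wide is the Indeterminate route?* The death must be unwitnessed, the participant found more than 24 hours after last being seen, with no autopsy and no other information. A strip could matter only if the vest was also being worn and had recorded the event.

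**What a breach would do (illustration; arm counts are assumed)**

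Inputs: N = 2300 and a pooled rate of 1.66% (protocol 1.5.12), 2:1 allocation, hence 1533 vest and 767 control; 2300 × 0.0166 = 38 events. Test: uncorrected chi-square (SAP section A).

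- *Scenario A.* Rates of 1.18% and 2.62% satisfy both the pooled rate, (2 × 1.18 + 2.62)/3 = 1.66%, and 70% power. Events: 1533 × 0.0118 = 18.1 and 767 × 0.0262 = 20.1, so 18 v 20.
- *Scenario B.* Design rates of 1.02% and 3.0%. Events: 1533 × 0.0102 = 15.6 and 767 × 0.030 = 23.0, so 16 v 23.

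| Scenario | Vest deaths moved | Vest v control events | p |
|---|---|---|---|
| A | 0 | 18 v 20 | 0.011 |
| A | 2 out | 16 v 20 | 0.004 |
| A | 2 in | 20 v 20 | 0.024 |
| A | 4 in | 22 v 20 | 0.048 |
| A | 5 in | 23 v 20 | 0.065 |
| B | 0 | 16 v 23 | 0.0006 |
| B | 5 in | 21 v 23 | 0.007 |
| B | 10 in | 26 v 23 | 0.041 |
| B | 11 in | 27 v 23 | 0.055 |

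Each move shifts the risk ratio by (1/1533)/(20/767) = 0.025 in A and (1/1533)/(23/767) = 0.022 in B.

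With no true effect and 1.66% in both arms, taking four deaths out of the vest arm gives 0.0166 − 4/1533 = 1.40% there. By normal approximation this raises the two-sided rejection rate from 5% to about 8.5%. Adding four gives about 6.7%.

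A systematic breach would therefore matter. But every row with a move requires LifeVest strips to be used against the ban, and the documents give no reason to expect any particular number.

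**The case for a change.** The best case for a change is that the definition of a primary endpoint should not leave precedence to be inferred from another paragraph. The word *device* is not used consistently: the Quality of Life text in 1.5.9 uses it for the LifeVest. Existing ICDs are excluded and early ICDs are expected to be rare, so the LifeVest is the likeliest arrhythmia recorder within 90 days. Site staff remove references to treatment only as far as they can. Electrophysiologists also read LifeVest strips for the arrhythmia outcomes, and no text says that they are different people from the death adjudicators. Two added phrases would cost nothing.

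What stands is that the wording is unqualified and a cross-reference is missing. The rest does not carry over into a consequence. Imperfect stripping at the site is followed by central redaction. If rhythm information leaked through a discharge summary, or through a reader's memory of a strip, that would be a failure of redaction or of panel separation, and rewording the definition would cure neither. Nor would limiting the clauses to other devices guarantee symmetry. Section 1.5.5 blinds clinicians to LifeVest arrhythmias partly to prevent early ICD implantation, yet allows unblinding, so ICD data could also differ somewhat between arms.

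**Conclusion.** No change to the plan follows. This is a missing cross-reference within one section. The ban already decides which rule applies: it is explicit and reasoned, it covers all deaths, and it agrees with the packet procedure and the Table 3 sources. The suggested wording would restate a rule the plan already has, and would leave the sample size, the test and every event classification unchanged.

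Followed as written, the effect on the primary result is nil. The five (A) to eleven (B) deaths needed to lose significance describe a breach of protocol under assumed counts, not a property of the plan. The conclusion rests on two assumptions: that the coordinating centre builds and redacts packets as section 1.5.9 describes, and that *device* in the definition is read in line with the ban. A sponsor amending the protocol for other reasons could add a pointer to the ban for tidiness; nothing depends on it.
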